Sample size calculations were conducted using PASS 2019 Power Analysis and Sample Size Software (NCSS, Kaysville, Utah, USA). The effect size for the warning label was hypothesized to be the smallest effect size, and so the sample size was chosen to power this effect. With this sample size, the power associated with the tax and combined conditions will be maintained at approximately the same level or higher (better). For a factorial design with two factors at 2 and 2 levels, assuming a Cohen's d of 0.1 (considered "small",²⁸ and conservative relative to SSB warning label experiments which found 0.25),²⁹ the sample size per arm needed to achieve 80% power at an alpha level of 0.05 is $n=786$ per arm ($n=3,144$ total across the four arms).

Outliers and Exclusions

To complete the shopping task, a participant's shopping basket must have +/- 2 items of the total number of items on the shopping list. There are 9 items total on the shopping list, so the participant's basket must have 7-11 items.

We will conduct sensitivity analyses excluding individuals who are in the bottom 2 percentile of expenditures, those who complete the study unusually quickly (e.g., based on the distribution of time to completion as ascertained during a soft launch of the study), and individuals who are non-compliant with the shopping list (<50% of products selected comply with the shopping list).

SAFETY MANAGEMENT

Provided that this study is conducted completely online, and participants do not have any interactions with study staff there is no anticipation of adverse events. However, the investigators have provided an email to contact as well as the IRB contact information, on the consent form, should a participant be concerned about any aspects of the research study.

DATA COLLECTION AND MANAGEMENT

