Developing and Evaluating Product Messaging

Hypotheses and Analytic Plan

NCT# NCT04716010

Version Date: 6/01/21

Hypotheses

The overall purpose of this study is to assess the impact of taxes, warnings, and a combination of taxes and warnings on US adults' decisions to purchase products that contain red meat in an online grocery store.

Primary Outcomes

The co-primary outcomes are the count of products that contain red meat and the percent of products in the shopping basket that contain red meat. We will report both count and percent of products that contain red meat.

We hypothesize that:

1. Compared to the control (no taxes and no warnings), both taxes and warnings will lead to reduced purchases of products that contain red meat.
2. The combination of taxes and warnings will lead to a larger reduction in purchases of products that contain red meat than taxes or warnings alone.

Secondary Outcomes

We hypothesize that the taxes condition, warnings condition, and taxes and warning condition will lead to:

Behavioral

- A) Decrease in total saturated fat of products purchased
- B) Decrease in total sodium of products purchased
- C) Decrease in total calories of products purchased

Psychological

- D) Decrease in perceived healthfulness of eating red meat
- E) Increase in perceived risk of cancer from eating red meat
- F) Increase in perceived environmental harms of eating red meat
- G) Increase in thinking about the health harms of food products
- H) Increase in thinking about the environmental harms of food products
- I) Increase in thinking about the price of food products
- J) Decrease in perceived healthfulness of specific red meat products
- K) Increase in perceived environmental harm of specific red meat products
- L) Increase in perceived cost of specific red meat products
- M) Increase in intention to reduce red meat consumption

Other Outcomes reported by condition

We hypothesize that the taxes condition, warnings condition, and taxes and warning condition will lead to:

- N) Increase in policy support for taxes on red meat products
- O) Increase in policy support for health warnings on red meat products
- P) Increase in policy support for environmental warnings on red meat products

Other Outcomes not reported by condition

- Q) Acceptability of the online grocery store
- R) Ease of use of the online grocery store

STATISTICAL CONSIDERATION

Statistical Methods

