First, we will conduct a soft launch of 200 participants. With the data from the 200 participants, we will run descriptive analyses of the primary, secondary, and other outcomes, and we will confirm randomization is working properly.

If randomization is working properly and there are not apparent issues with the data collection (e.g. technical issues with the online store software), we will resume data collection until the final sample is achieved. The original 200 participants from the soft launch will be included in the final dataset.

If randomization is not working properly and/or there are apparent issues with the data collection (e.g., erroneous skip patterns), we will address all identified issues then resume data collection until the final sample is achieved. The original 200 participants from the soft launch will not be included in the final dataset.

We will descriptively report unadjusted values for primary, secondary, and other outcomes.

We will use a two-sided critical alpha of 0.05 to conduct all statistical tests. Per CONSORT guidelines, we will not test for balance in covariates. Primary analyses will be intent-to-treat, including all eligible participants with non-missing outcome data (e.g., complete-case).

Sensitivity Analyses

We will describe dropout (defined as entering the store but not completing the purchasing task) by study arm and by screener characteristic (age, red meat consumption). If differential dropout is identified, we will consider sensitivity analyses to handle missing outcome data, such as inverse probability weighting.

For all primary, secondary, and other outcomes, we will assess whether the outcomes vary by study arm with regression models, in which the referent group will be the control (compared to each of the three interventional study arms). For the primary outcomes, the regression model will be selected based on the frequency of zero purchases of products containing red meat. If the frequency of zeros is high (>10% of participants), we will consider models to deal with the high proportion of zeros (e.g., zero-inflated Poisson or zero-inflated negative binomial for a count variable; fractional regression for percentage variable). Choice of model will also depend on whether heteroscedasticity exists. Model selection exercises will be reported. For secondary and other outcomes, we will use linear regression.

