For all analyses, means will be compared between each of the treatment groups and the control group, and for the primary outcome all pairwise comparisons of means will be examined. We will consider a result statistically significant at $p < 0.05$.

In exploratory analyses, we will examine whether the following participant characteristics moderate the intervention effects on the primary outcomes:

- a. Frequency of red meat intake
- b. Interest in health
 - For interest in health, we will take the average of the 3 items if $\alpha > .70$. The 3 items are adapted from Hearty et al. (2006). If α is not above .70, we will either create a scale excluding the item that makes the three-item scale drop below .70, if there is one; or we will look at the items separately.
- c. Interest in sustainability
 - For interest in sustainability, we will take the average of the 6 items if $\alpha > .70$. The six items are adapted from Haws et al. (2014). If α is not above .70, we will either create a scale excluding the item(s) that make(s) the six-item scale drop below .70, if there is one; or we will look at the items separately.
- d. Household income level
- e. Educational attainment

- f. Age group
- g. Race/ethnicity
- h. Political orientation
- i. Gender

To test whether these characteristics moderate the effect of the intervention on the count or percentage of products containing red meat selected, we will fit a series of regression models (one for each potential moderator), with trial arm, the moderator (specified as dummy variables), and their interaction as predictors. We will use a Wald chunk test to determine the joint interaction. We will quantitatively evaluate the presence of moderation by calculating the marginal effect of the intervention on the outcome at different levels of the moderating variable. If the pattern of main results is similar between intervention arms (warning label, tax, and warning plus tax), we will consider combining intervention arms for the moderation analysis.

Sample Size and Power

Sample size calculations were conducted using PASS 2019 Power Analysis and Sample Size Software (NCSS, Kaysville, Utah, USA). The effect size for the warning label was hypothesized to be the smallest effect size, and so the sample size was chosen to power this effect. With this sample size, the power associated with the tax and combined conditions will be maintained at approximately the same level or higher (better).

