For a factorial design with two factors at 2 and 2 levels, assuming a Cohen's *d* of 0.1 (considered "small" (Cohen, 1988), and conservative relative to SSB warning label experiments which found 0.25 (Grummon & Hall, 2020)), the sample size per arm needed to achieve 80% power at an alpha level of 0.05 is $n=786$ per arm ($n=3,144$ total across the four arms).

Outliers and Exclusions

To complete the shopping task, a participant's shopping basket must have +/- 2 items of the total number of items on the shopping list. There are 9 items total on the shopping list, so the participant's basket must have 7-11 items.

We will conduct sensitivity analyses excluding individuals who are in the bottom 2 percentile of expenditures, those who complete the study unusually quickly (e.g., based on the distribution of time to completion as ascertained during a soft launch of the study), and individuals who are non-compliant with the shopping list (<50% of products selected comply with the shopping list).

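### The stated 80% power for the warning effect at d = 0.1 fits a pooled factorial contrast that is not planned; the planned warnings v control test has about 51%

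*SAP*

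**What the plan says.** Under Sample Size and Power, both documents take the warning label to have the smallest effect of the interventions, and the SAP adds that "the sample size was chosen to power this effect". The calculation is introduced with "For a factorial design with two factors at 2 and 2 levels" and uses Cohen's d of 0.1. It concludes that "the sample size per arm needed to achieve 80% power at an alpha level of 0.05 is" 786, giving 3,144 over four arms. For the other interventions, the SAP says that "the power associated with the tax and combined conditions will be maintained at approximately the same level or higher (better").

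The analysis text, under Statistical Consideration, describes different contrasts. Every outcome is modelled by regression "in which the referent group will be the control (compared to each of the three interventional study arms"). The SAP then lists the contrasts to be tested: "means will be compared between each of the treatment groups and the control group, and for the primary outcome all pairwise comparisons of means". Hypothesis 1 is framed against the single arm with neither tax nor warnings. Hypothesis 2 is that the combination "will lead to a larger reduction in purchases of products that contain red meat than taxes or warnings alone". Arms are pooled in one place only, the exploratory work on effect modifiers: "we will consider combining intervention arms for the moderation analysis". The protocol carries the same sample size and analysis text.

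**The concern.** A 2x2 factorial calculation gains its efficiency by using all four arms to estimate each factor's effect. A comparison of one arm with control uses only half of the participants. If the sample is sized for the first and the analysis does the second, the stated power does not belong to the planned test.

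This is the only power statement in the trial, and it concerns the effect on which the trial was sized. A reader who meets a non-significant warnings result and relies on the stated 80% would take the chance of missing an effect of 0.1 to be 20%. For the planned test it is about 49%. Combination v tax, which is part of hypothesis 2, is in the same position if warnings add 0.1 on top of the tax.

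**Working it through.** **Inputs.** d = 0.1 (so SD = 1), 80% power, alpha 0.05 and n = 786 per arm come from Sample Size and Power. Two-sided testing comes from Statistical Methods. Equal allocation comes from the protocol's Study Design section. No dropout allowance is stated, so the data are taken as complete.

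**Step 1: reproduce the plan's figure.** For a one-degree-of-freedom term in a 2x2 design, Cohen's f = d/2 = 0.05, the noncentrality is 4n × f², and the residual degrees of freedom are 4n − 4. The noncentral F distribution gives:

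- n = 785 per arm: power 0.7998
- n = 786 per arm: power 0.8003

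So 786 is the smallest n per arm that reaches 80%. The normal approximation for 1,572 v 1,572 agrees: SE = √(2/1572) = 0.03567; 0.1/0.03567 = 2.804; power = Φ(2.804 − 1.960) = Φ(0.844) = 0.80.

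**Step 2: try other readings at 786 per arm.**

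| Reading | Power |
|---|---|
| Three-degree-of-freedom test of four arms, f = 0.05 | 0.645 |
| Two arms, one-sided, d = 0.1 | 0.632 |
| Two arms, two-sided, d = 0.1 | 0.509 |

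None gives 80%. The documents do not name the term or procedure, so the main-effect reading is an inference. An interaction term with f = 0.05 would also need 786 per arm, but that is not a planned test either.

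**Step 3: power of the planned test, 786 v 786.** SE = √(2/786) = 0.05044; 0.1/0.05044 = 1.982; power = Φ(1.982 − 1.960) = Φ(0.022) = 0.509. The noncentral t distribution gives 0.5085, or 0.5088 with the four-arm residual degrees of freedom (3,140). Across effect sizes (noncentral t):

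| True d | Power |
|---|---|
| 0.05 | 16.8% |
| 0.075 | 31.8% |
| 0.10 | 50.9% |
| 0.125 | 69.7% |
| 0.14 | 79.2% |
| 0.15 | 84.4% |
| 0.20 | 97.7% |
| 0.25 | 99.9% |

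**Step 4: what 80% would take.** The effect detectable with 786 per arm is (1.960 + 0.842) × 0.05044 = 0.141. To detect d = 0.1, n = 2 × (1.960 + 0.842)² / 0.1² = 1,570 per arm. Noncentral t gives 1,571, which is 4 × 1,571 = 6,284 in all.

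**Step 5: combination v tax.** The documents give no figure for what warnings add to the tax, so the range is an assumption. If the effects are additive the increment is 0.10 and power is 50.9%. At 0.075 it is 31.8%, and at 0.05 it is 16.8%.

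**The case against.** The strongest reply is that the calculation is right on its own terms. It says openly that it is factorial, the four arms do form a 2x2, and 0.1 was chosen as cautious beside the 0.25 cited from experiments with drink warnings. At 0.20 or 0.25 the planned two-arm test has 97.7% or 99.9% power, and the detectable effect of 0.141 is still well below 0.25. The arms, estimates and tests stay as they are, so the harm arises only if the warnings result is non-significant and is then read against the stated power. The sentence on the tax and combined conditions is most naturally about each against control, and does not expressly promise power for combination v tax. Finally, the primary model is still open, so power for a comparison of means is only a guide.

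Much of this stands. The arithmetic is not wrong; the mismatch lies between the calculation and the analysis. The problem is limited to effects near 0.1, and the combination v tax figures rest on assumed increments. None of it makes the 80% a property of the planned test. The plan itself chose 0.1 as the planning value, and its analysis text names its contrasts without including a pooled one. A main effect averages the warning effect over the two tax conditions. It equals warnings v control only if there is no interaction, and neither document makes that assumption for the primary analysis. The plan's own calculation is in Cohen's d, so comparing means is like for like.

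**Conclusion.** The concern holds. The 80% at d = 0.1 belongs to a pooled contrast of 1,572 v 1,572 (or another one-degree-of-freedom factorial term) that neither document plans. The planned test of the effect on which the trial was sized, 786 v 786, has 50.9% power at that effect and reaches 80% at d of about 0.141.

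These figures assume a comparison of two means, two-sided alpha 0.05 without adjustment, equal arms and complete data. Losses under the complete-case analysis could lower power further; the documents do not say whether 3,144 counts people randomised or people who complete. A zero-inflated or fractional model could change the figures. Which factorial term was run is inferred, but the 51% does not depend on that inference.

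**What to change.** In Sample Size and Power of both documents, replace the power statement with wording such as:

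> For a two-arm comparison of means with complete data and two-sided alpha 0.05, 786 per arm gives about 80% power at d = 0.141 and 51% at d = 0.10.

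Limit the sentence on the tax and combined conditions to tax v control and combination v control, relative to the restated power for warnings. It should not be taken to cover combination v tax: ranking warnings as the smallest effect against control says nothing about what warnings add to a tax.

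Optionally, prespecify the contrasts that the calculation fits: warnings (arms 2 and 4 v arms 1 and 3) and tax (arms 3 and 4 v arms 1 and 2), each reported with the interaction estimate. Each has 80% power at d = 0.1. The text should say that they estimate an effect averaged over the other factor, which equals the arm v control effect only without interaction.

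The cost is wording in two documents and a less favourable power statement. No participants are added, and the optional contrasts are two more estimates from data already to be collected.
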